Protocol title:

Feasibility of using daily Humidified Nasal High-flow with Oxygen during Sleep and/or Daytime in Hypercapnic COPD patients following recent (< 12 wks.) hospitalization for AECOPD for 90 days

NCT03221387

Date: 10/06/2017

1) Abstract of the study

Humidified Nasal High-flow with Oxygen (HNHF-O2) therapy has been reported to have acute beneficial effects in patients with hypoxemic respiratory failure. HNHF-O2 may be beneficial in patients with COPD and chronic impairments in gas exchange, both hypoxemia as well as hypercapnia. HNHF-O2 may decrease work of breathing, reduce dyspnea, improve airway humidification, and potentially stabilize or reduce carbon dioxide levels. However, there is limited data showing the chronic effects of HNHF-O2 in patients with hypercapnic respiratory failure, specifically those discharged to home following hospitalization for an acute exacerbation. Data that demonstrates that HNHF-O2 is well tolerated, and stabilizes or improves gas exchange long term in patients with COPD is lacking. Similarly, data that demonstrates that this therapeutic regimen is feasible to provide to patients in the home environment are lacking. This is an open-labeled pilot study of thirty patients to determine the safety and feasibility of using the device in the outpatient management of patients with COPD.

2) Protocol Title

Feasibility of using daily Humidified Nasal High-flow with Oxygen during Sleep and/or Daytime in Hypercapnic COPD patients following recent (< 12 wks.) hospitalization for AECOPD for 90 days

3) IRB Review History

Not applicable

4) Investigator

[name]

5) Objectives

To assess the feasibility of using daily home HNHF-O2 during sleep and/or daytime in hypercapnic COPD patients following recent (< 12 weeks) hospitalization for AECOPD for 90 days.

6) Background

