We treat an average of 16,000 outpatients a year; over 50% of these patients carry a diagnosis of advanced lung disease, including COPD, IPF, pulmonary hypertension, and bronchiectasis. We are a major referral center for lung volume reduction surgery.

All physicians, nurses and ancillary staff members will be instructed in the details of this study.

9) Prior Approvals

Not applicable.

10) Study Design

a) Recruitment Methods

Thirty patients hospitalized for acute exacerbation of COPD \leq the last 12 weeks will be enrolled into the study. Subjects will be recruited from the Temple Lung Center clinical practices in Philadelphia and Oaks, PA.

Potential subjects will be recruited during scheduled office visits to the Temple Lung Center offices in Philadelphia and in Oaks, PA. Many of these patients will be those who have been referred to Temple. We will also contact pulmonology practices in the tri-state area through direct mailings and our monthly research fax blast. The Temple Lung Center also maintains an IRB-approved registry of patients who have agreed to be contacted to discuss participation in clinical research trials.

Describe materials that will be used to recruit subjects. Include copies of these documents with the application. – Not applicable

Subjects will receive compensation in the form of a \$25 gift card for each completed visit during their participation in this study.

b) Inclusion and Exclusion Criteria

Consecutive patients \geq 40 years of age or older who are admitted to the hospital for an acute exacerbation of COPD within the past 12 weeks. Patients will have COPD as the primary diagnosis and have smoked > 10 pack years. Patients should be receiving supplemental oxygen as part of their usual clinical care.

Patients must be willing to give informed consent and be willing to participate in measurement of ABGs, brief history and physical examination and answer questionnaires regarding daily use of HNHF-O2 therapy. Women who are pregnant are excluded from this research. Women of childbearing potential will have a urine pregnancy test to ensure that they are not pregnant.

The main exclusion criteria are upper airway or nasal problems that prohibit the use of high flow oxygen and patients with any of the following will be excluded:

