current use (\leq 4 weeks of study entry) of any PAP-therapy (e.g., CPAP or NPPV); sleep apnea as follows: STOPBang scores \geq 5 or STOPBang score \geq 2 plus BMI $>$ 35 kg/m²; or Berlin questionnaire scores suggesting high likelihood of sleep apnea with increased risk of sleep-related accident (e.g., occupation as a commercial driver or pilot); or excessive daytime sleepiness (i.e., either of High (>15) score on the Epworth Sleepiness Scale or “fall asleep” accident or “near miss” accident in prior 12 months).

c) Local Number of Subjects

Thirty subjects will be accrued locally for this study.

We expect few screen failures.

d) Study-Wide Number of Subjects

If this is a multicenter study, indicate the total number of subjects to be accrued across all sites. – Not applicable.

e) Study Timelines

- Subjects will be followed for 90 days with regular telephone follow-up and clinic visits throughout.
- Subjects will be enrolled over a period of 12 months.
- The investigators will complete the data analysis approximately 18 months after the first subject is enrolled.

f) Study Endpoints

The primary endpoints of this study are the feasibility of oxygen therapy by HNHF-O2 at home over a 90-day period in terms of tolerance and hours of use. Descriptive statistics will be used to characterize the patient population in terms of demographic factors and severity of airflow obstruction. Changes in PaO₂, PaCO₂ and pH across the days will be done by analysis of variance. The effect of baseline PaCO₂ on change in PaCO₂ with HNHF-O2 therapy will be analyzed as an independent effect on change in PaCO₂ levels with HNHF-O2. Changes in respiratory rate, heart rate, blood pressure accessory muscle use will also be assessed by analysis of variance. Patient tolerance and side effects will also be measured across days of use per patient and across days in all patients as group trends. Hours of use per device log and per patient diary will be independently analyzed and compared to one another. The impact on change in exacerbation frequency and severity will be analyzed. Changes in spirometry, 6MWD, GOLD grade and class and BODE scores prior to and after 90 days of HNHF-O2 will be analyzed.

g) Procedures Involved in the Human Research

[figure not shown]
An overview of the study is provided in the figure below.

Outpatient HNHF-O2 Protocol

Version 3.0

10/06/2017

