Feasibility of using daily home HNHF-O2 during Sleep and/or Daytime in Hypercapnic COPD patients following recent (< 12 wks.) hospitalization for AECOPD for 90 days

¹ > 40 yrs. Age and Hospitalized for AECOPD; able to sign IC and willing to do tests

² vital signs, respiratory patient discomfort, Likert scale for clinical improvement, dyspnea (modified Borg Score, mMRC) ABG 5 minutes after inspiring O₂ to maintain SaO₂ >90%, spirometry, 6 MWT, questionnaires (CAT, SGRQ), set baseline diary for respiratory symptoms

³ Inquire about any problems and assess for adherence, troubleshoot

⁴ vital signs, respiratory patient discomfort, Likert scale for clinical improvement, dyspnea, side effects of HNHF-O₂, and review daily electronic diary of respiratory symptoms

⁵ Same as #2

Patients who have had a recent COPD exacerbation (<12 weeks since discharge) accompanied with respiratory failure who meet the above inclusion criteria will be considered for participation in the study.

Once informed consent has been obtained patients will be given the opportunity to participate in the sleep substudy until the enrollment goal of ten subjects has been achieved. A separate protocol and consent form has been submitted for this study. The following procedures will be performed as part of the main study:

Outpatient HNHF-O2 Protocol

Version 3.0

10/06/2017

Test	Visit 1 Screening	Visit 1a Baseline	Visit 2 Clinic Placed on HNHF-O2	Visit 3 Phone Call Day 1	Visit 4 Phone call Day 3 ± 3	Visit 5 Clinic Day 7 ± 5	Visit 6 Phone call Day 17 ± 3	Visit 7 Clinic Day 28 ± 5	Visit 8 Phone call Day 37 ± 3	Visit 9 Clinic Day 49 ± 5	Visit 10 Phone call Day 58 ± 3	Visit 11 Clinic Day 70 ± 5	Visit 12 Phone call Day 80 ± 3	Visit 13 Clinic Day 90 ± 5
Screen	X													
Informed Consent	X													
History & Physical		X				X		X		X		X		X
Pregnancy test for women of childbearing potential		X												
Arterial blood gas◆		X	X											x
Pre- and Post- Bronchodilator Spirometry		X												X
6 minute walk distance		X												X
mMRC Questionnaire		X ²												
Borg Questionnaire		X ²	X			X		X		X		X		X
Assess Accessory Muscle use		X	X			X		X		X		X		X
Assess subject comfort		X	X			X		X		X		X		X

Outpatient HNHF-O2 Protocol

Version 3.0

10/06/2017

Test	Visit 1	Visit 1a	Visit 2	Visit 3	Visit 4	Visit 5	Visit 6	Visit 7	Visit 8	Visit 9	Visit 10	Visit 11	Visit 12	Visit 13

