At baseline, patients will have measurement of vital signs (heart rate, respiratory rate and blood pressure), dyspnea (modified Borg score, mMRC) arterial blood gas after 5 minutes of inspiring supplemental oxygen to keep $\text{SaO}_2 > 90\%$, and use of accessory muscles of ventilation. Patients will have spirometry performed pre-and post-bronchodilator administration. Patients will have assessment of their current respiratory health by completing CAT, mMRC and SGRQ questionnaires. A detailed history of their exacerbation frequency and severity will be obtained. Patients will perform a 6-minute walk test. Patients GOLD grade and group will be classified and patients BODE scores will be calculated.

Patients will be queried regarding the presence and magnitude of complaints of cough and sputum production by using a daily electronic diary for a 2-week period of run in. After the 2-week run-in period the patient will be scheduled to return to initiate HFNC with oxygen therapy.

Electronic daily diary of respiratory symptoms.

- ❖ Breathlessness (Modified Borg Scale)
- ❖ Sputum Quantity, Color, and Consistency
- ❖ Peak Flow Measurements
- ❖ Presence of Temperature Over 100°F
- ❖ Presence of Any Cough, Wheeze, Sore Throat or Nasal Congestion

Outpatient HNHF-O2 Protocol

Version 3.0

10/06/2017

Patients will be seen in clinic and instructed in the use of HNHF-O2 and its proposed benefits. The necessity of compliance and adherence to the treatment plan will be emphasized.

Following the outpatient clinic visit, patients will be set up at home using an established home vendor for respiratory equipment. Patients will continue to report their daily respiratory symptoms via the electronic diary.

Post placement on optimal dose of HNHF-O2 therapy, subjects will be called the next day to determine if there were any problems.

Patients will report to clinic at baseline and then 7 ± 2 , 28 ± 5 , 49 ± 5 , and 70 ± 5 days for the following assessment:

- Measurements of vital signs (heart rate, respiratory rate and blood pressure)
- Respiratory patient-discomfort and dyspnea assessed using an unmarked 100 mm visual analogic scale from “no discomfort” to “maximal imaginable discomfort”
- Likert scale model indicating marked improvement (+2), slight improvement (+1), no change (0), slight deterioration (-1) and marked deterioration (-2)

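### In this single-arm study no before-after analysis uses time since discharge, so recovery from the exacerbation cannot be told apart from change on HNHF-O2

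*Combined protocol and SAP*

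**What the plan says.** The abstract sets out the design: "This is an open-labeled pilot study of thirty patients to determine the safety and feasibility of using the device". No control group is described anywhere.

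Section 10(g) admits "Patients who have had a recent COPD exacerbation (<12 weeks since discharge) accompanied with respiratory failure". Section 10(b) counts from a different event, taking patients "who are admitted to the hospital for an acute exacerbation of COPD within the past 12 weeks". Neither section sets a minimum interval or a stability requirement. On the run-in, 10(g) states: "After the 2-week run-in period the patient will be scheduled to return to initiate HFNC with oxygen therapy". Follow-up on the device then lasts 90 days (10(e)).

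The analyses are in 10(f) and are repeated in 10(i):

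- Blood gases: "Changes in PaO₂, PaCO₂ and pH across the days will be done by analysis of variance". Vital signs and accessory muscle use are treated the same way.
- Function and staging: "Changes in spirometry, 6MWD, GOLD grade and class and BODE scores prior to and after 90 days of HNHF-O2 will be analyzed".
- Covariates: the only one named is baseline PaCO2, for one outcome: "The effect of baseline PaCO₂ on change in PaCO₂ with HNHF-O2 therapy will be analyzed as an independent effect".
- Exacerbations: the change in frequency and severity is to be analysed as an impact.

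In the schedule table, spirometry, 6MWD and BODE are measured at Visit 1a (before the run-in) and at Day 90. Arterial blood gas, Borg, accessory muscle use and comfort are measured at Visit 1a, at Visit 2 (when the device is placed) and at Day 90.

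**The concern.** A patient who starts the device two weeks after discharge may still have much of the recovery ahead. One who starts at 14 weeks probably has little. The plan pools them, and without a control arm nothing else in the analysis stands in for what would have happened without the device. A mean improvement at Day 90 would then mix any device effect with natural recovery, in a proportion set by how early patients happened to enrol.

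Baseline PaCO2 is not a substitute. A high value may be stable chronic hypercapnia or incomplete recovery, and only the interval since discharge helps to tell these apart. What is at stake is how the secondary results can be read, including any use of them to plan a later trial.

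**Working it through.** **Inputs from the documents.** Entry at 0 to under 12 weeks since discharge and a 2-week run-in (10(g)); 90 days on the device (10(e)); 30 evaluable patients (10(i)). The plan gives no SD, effect size or power for any before-after change, so it has no figure of its own to reproduce on this point.

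**Timing.** Device start runs from 0 + 2 = 2 weeks to 12 + 2 = 14 weeks after discharge. For measures with Visit 1a as their only baseline, the before-after interval is 14 + 90 = 104 days.

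**Assumptions (not in the documents).** No device effect. Entry is uniform over the window. PaCO2 at discharge is A mmHg above its stable level, and the excess decays exponentially with half-life h, so k = ln 2 / h. SD of change is 6 mmHg.

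**Natural fall from Visit 2 to Day 90**, for device start at week w: A × e^(−kw) × (1 − e^(−k·90/7)).

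- h = 3, k = 0.231, w = 2: 0.630 × 0.949 = 0.598 of A, or 2.4 mmHg (A = 4) to 4.8 mmHg (A = 8). At w = 14: 0.0394 × 0.949 = 0.037 of A, or 0.15 to 0.30 mmHg.
- h = 6, k = 0.1155, w = 2: 0.794 × 0.774 = 0.614 of A, or 2.5 to 4.9 mmHg. At w = 14: 0.198 × 0.774 = 0.153 of A, or 0.6 to 1.2 mmHg.

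Averaged over weeks 2 to 14, e^(−kw) is (0.630 − 0.039)/(12 × 0.231) = 0.213 for h = 3, and (0.794 − 0.198)/(12 × 0.1155) = 0.429 for h = 6. The mean fall is therefore 0.213 × 0.949 = 0.202 of A, or 0.429 × 0.774 = 0.332 of A. The standard error is 6/√30 = 1.10 mmHg.

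**Simulated trials, n = 30.** False falls are counted in one direction at a nominal 2.5%. The crude test is a one-sample t-test of change. The week-14 estimate comes from a linear regression on w.

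| A (mmHg) | h (weeks) | Mean natural fall | False falls, crude | False falls at week 14 | Slope significant |
|---|---|---|---|---|---|
| 2 | 3 / 6 | 0.4 / 0.7 | 5% / 8% | 2% / 3% | 6% / 6% |
| 4 | 3 / 6 | 0.8 / 1.3 | 11% / 21% | 2% / 4% | 8% / 7% |
| 6 | 3 / 6 | 1.2 / 2.0 | 19% / 40% | 2% / 5% | 11% / 10% |
| 8 | 3 / 6 | 1.6 / 2.7 | 28% / 64% | 2% / 6% | 17% / 15% |

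**Run-in share for spirometry, 6MWD and BODE.** Averaging the same curve over entry at weeks 0 to 12, the change from Visit 1a to Day 90 is 0.125 (run-in) + 0.202 (on device) = 0.327 of the deficit at discharge for h = 3, and 0.112 + 0.332 = 0.444 for h = 6. Between a quarter and two fifths of the apparent change (0.112/0.444 = 25%; 0.125/0.327 = 38%) would precede the device. This is in units of the deficit; the documents give nothing from which to express it in litres, metres or BODE points.

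**What a covariate can do.** Centred at its mean, the interval leaves the estimated mean change exactly equal to the crude one, so the bias in that mean stays. Reading the model at week 14 brings false falls down to 2–6%, at a price:

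- The standard error rises from about 1.1 to 2.2 mmHg, and to about 9.8 if entry clusters in weeks 2–6.
- Detection of a true 3 mmHg fall with no recovery drops from about 75% to about 26%.
- With h = 3 the linear form gives a mean rise of 0.2–0.4 mmHg at week 14, where the true value is a small fall.

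**The case against.** The strongest reply is that the plan makes no efficacy claim. Section 10(i) says the study is not meant to test efficacy, the primary endpoints are tolerance and hours of use, and neither is a before-after measure. No success rule hangs on the secondary changes. This stands, and it lowers the priority of the point. It does not remove it, because 10(f) still commits to these analyses and words them as change with the therapy or as its impact.

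Second, the size is assumed. With 2 mmHg of recovery the false-fall rate is little above nominal, and with none it is nominal. Recruitment at scheduled office visits also makes uniform entry from week 0 unverified. This stands too.

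Third, time since discharge is not the only handle. Visit 1a, Visit 2 and the run-in diary give device-free information within patients. That is correct, but the plan does not say it will use them, and they do not cover recovery after Visit 2.

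Two stronger readings are tempting. A reader might infer that the trial's conclusion will credit recovery to the device; the documents support only that the two cannot be separated in the secondary outcomes. A reader might also infer that adjusting for the interval, or reading the model at the late end of the window, would license attribution to HNHF-O2. The working shows that it would not at n = 30: the late estimate is imprecise and depends on linearity, and a control group is still missing.

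**Conclusion.** The point holds as a low-cost improvement to the secondary analyses. The window, the run-in, the single arm and the lack of any term for time since discharge are all in the text. Together they mean that recovery after the exacerbation cannot be distinguished from change on HNHF-O2.

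The size is conditional: about 11–64% false falls in PaCO2 if the excess at discharge is 4–8 mmHg with a half-life of 3–6 weeks, SD 6 mmHg and uniform entry, and about 5–8% if the excess is 2 mmHg. The documents supply none of these values. The primary endpoints are not touched.

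**What to change.** In 10(f) and 10(i):

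1. Record weeks from discharge to each measure's baseline and to device start. Reconcile 10(b), which counts from admission, with 10(g), which counts from discharge, so that the window and this interval are well defined.
2. Add the interval as a term in each Day 90 change analysis. Report the crude change, the slope with its confidence interval, and the change by interval since discharge.
3. Use Visit 2 as the pre-device reference for blood gas, Borg, accessory muscle use and comfort, and show the Visit 1a to Visit 2 drift. For this, state that the Visit 2 measures precede first use of the device. Also reconcile the baseline blood gas condition: the text of 10(g) describes supplemental oxygen, while the schedule footnote describes room air.
4. Give the late-window estimate only as a sensitivity analysis, not as the rule for attribution.
5. Describe all changes as uncontrolled, not as the effect or impact of HNHF-O2.

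The cost is wording, a little more analysis and one date that 10(g) already needs for eligibility; no visit or test is added. The slope and the late-window estimate will be imprecise with 30 patients. In the settings with 4–8 mmHg of recovery the slope was significant in only 7–17% of trials, so a null slope does not rule out recovery.

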	Screening	Baseline	Clinic Placed on HNHF- O2	Phone Call Day 1	Phone call Day 3 ± 3	Clinic Day 7 ± 5	Phone call Day 17 ± 3	Clinic Day 28 ± 5	Phone call Day 37 ± 3	Clinic Day 49 ± 5	Phone call Day 58 ± 3	Clinic Day 70 ± 5	Phone call Day 80 ± 3	Clinic Day 90 ± 5
Epworth Sleepiness Scale	X													
Berlin Sleep Questionnaire	X													
STOP-Bang Questionnaire	X													
St. George's Respiratory Questionnaire		X												X
GOLD Category		x												
BODE Index		X												X
Daily Diary	X	X	X			X		X		X		X		X
COPD Activity Test		X												X
Review current medications	X	X	X	X	X	X	X	X	X	X	X	X	X	X
Phone call				X	X		X		X		X		X	
Sleep substudy participants														
Insomnia Severity index		X												
Home sleep study		X ¹				X						X		
Epworth Sleepiness		X ²				X ²						X ²		

Outpatient HNHF-O2 Protocol

Version 3.0

10/06/2017

Scale														
-------	--	--	--	--	--	--	--	--	--	--	--	--	--	--

¹ For those subjects enrolled in the sleep substudy the acquaintance and baseline sleep studies must be completed before beginning HNHF-O2

² Questionnaires are done at baseline visit and repeated at home prior to the baseline, day 7, and day 70 sleep studies.

◆ For ABGs, the test will be done on room air after the participant has been off the Airvo device for 20 minutes. If the participant starts to desaturate, then it can be done on 2L of oxygen.

Outpatient HNHF-O2 Protocol

Version 3.0

10/06/2017

There will be collection of demographic data including age, gender, race, current medications, and comorbid conditions. A patient history of duration of the nature and course of prehospital symptoms, past medical history of smoking, and past use of respiratory medications and nonpharmacological therapy for COPD will be elicited. Historical collection of available clinical data including exacerbation history, reports of chest imaging as well as pulmonary function and/or exercise or cardiac data will be collected.

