- Side effects related to high flow nasal administration: nasal dryness, epistaxis, nasal crusting, eye discomfort, pressure discomfort, increase rhinitis, decreased smell, post nasal drip, hoarseness
- Hours of daily use of HNHF-O2 therapy
- Daily record keeping of daily diary review

At day 90 ± 2 the following will be measured:

- Measurements of vital signs (heart rate, respiratory rate and blood pressure)
- Respiratory patient-discomfort and dyspnea assessed using an unmarked 100 mm visual analogic scale from “no discomfort” to “maximal imaginable discomfort”
- Likert scale model indicating marked improvement (+2), slight improvement (+1), no change (0), slight deterioration (-1) and marked deterioration (-2)
- Side effects related to high flow nasal administration: nasal dryness, epistaxis, nasal crusting, eye discomfort, pressure discomfort, increase rhinitis, decreased smell, post nasal drip, hoarseness
- Hours of daily use of HNHF-O2 therapy
- Daily record keeping of daily diary review
- Arterial blood gas on room air after the participant has been off the Airvo Device for 20 minutes.
- Pre-and post-bronchodilator spirometry

Outpatient HNHF-O2 Protocol

Version 3.0

10/06/2017

- CAT, SGRQ
- 6 Minute walk test
- GOLD grade and group will be classified
- BODE scores will be calculated.

Application of HNHF-O2 therapy. During HNHF-O2, oxygen will be passed through a heated humidifier (myAIRVO 2, Fisher and Paykel Healthcare) and applied continuously through large-bore binasal prongs, with a gas flow rate of 20-35 liters per minute (or as high as tolerated). Temperature will be adjusted based on patient's comfort and range from 34-37 degrees based on prior experience. The fraction of oxygen in the gas flowing in the system will be adjusted to maintain an SpO2 of 90% or more. High-flow oxygen will be applied at the highest tolerated flow up to 35 lpm at home. Meter time and patient's log of hours of daily use will be measured and compared.

Hypercapnic COPD patients are encouraged to use supplemental oxygen therapy on a continuous basis. The use of the humidified nasal high-flow device in this protocol is not expected to change the total number of hours that the patient receives supplemental oxygen; however it will change the manner in which the oxygen is delivered. Patients will be encouraged to use the device for oxygen delivery as many hours per day as possible.

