In order to reduce the risk of contamination and extend the life of the tubing and patient interface it is recommended that the user clean the device at specified intervals. The patient interface should be washed in tap water and reconnected to the heated breathing tube. Thereafter, the device should be run in drying mode. This process takes about 90 minutes to complete and should be performed daily. On a weekly basis the heated breathing tube should be removed along with the patient interface and both washed in warm water with a mild detergent. The outside of the device should be wiped clean with a damp cloth. The inside of the heated breathing tube connection port should be cleaned with a low-lint cloth with mild dishwashing detergent.

The patient has the option to not receive supplemental oxygen during each of these cleaning procedures or to receive supplemental oxygen via a standard nasal cannula.

All supplies necessary for the maintenance of the device will be provided to the subject at no cost to them.

Study procedures:

History and physical exam, vital signs. These are all procedures routinely performed as standard of care.

Lung function testing (spirometry). Pre- and post-bronchodilator testing (spirometry) will be performed according to ATS standards. The bronchodilator

Outpatient HNHF-O2 Protocol

Version 3.0

10/06/2017

medication (albuterol) opens up the airways and will be used in lung function testing. This medication is often used to treat people with COPD. Spirometry will be performed by experienced study personnel.

Arterial blood gases. Arterial blood gases will be obtained from the radial artery in the wrist by experienced personnel. Blood gases will be obtained on room air after the patient has been off the Airvo device for 20 minutes.

6 minute walk test. Subjects will be asked to walk as far as they can for 6 minutes while receiving supplemental oxygen. Testing will be supervised by experienced study personnel with access to emergency medicine such as sublingual nitroglycerin, aspirin and albuterol.

Dyspnea questionnaires, accessory muscle use, and comfort assessments.

The Borg dyspnea questionnaire and mMRC are short questionnaires that can be completed in a minute or two. These questionnaires are included with this submission. Use of accessory muscles requires only subject observation.

Subject comfort assessments are also provided with this submission and can be completed in a minute.

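### Blood gases may be drawn on room air or on 2 L of oxygen depending on desaturation, and the analysis of PaO₂ change ignores which, so change can be misread in either direction

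*Combined protocol and SAP*

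**What the plan says.** The footnote to the arterial blood gas row of the schedule in 10(g), which is marked for Visits 1a, 2 and 13, sets the default: "For ABGs, the test will be done on room air after the participant has been off the Airvo device for 20 minutes". It then allows an exception: "If the participant starts to desaturate, then it can be done on 2L of oxygen". The exception is permissive and has no saturation threshold.

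Other parts of 10(g) differ:

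- The Day 90 list gives the default without the exception: "Arterial blood gas on room air after the participant has been off the Airvo Device for 20 minutes".
- The arterial blood gas paragraph under the study procedures does the same: "Blood gases will be obtained on room air after the patient has been off the Airvo device for 20 minutes".
- The baseline paragraph describes an "arterial blood gas after 5 minutes of inspiring supplemental oxygen to keep" SaO₂ above 90%. Note 2 to the overview figure agrees with it.

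The analysis is stated in 10(f) and repeated in 10(i): "Changes in PaO₂, PaCO₂ and pH across the days will be done by analysis of variance". Neither section mentions inspired oxygen. On the population, 10(b) says: "Patients should be receiving supplemental oxygen as part of their usual clinical care".

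**The concern.** PaO₂ depends on the oxygen being breathed. Under the footnote, low oxygenation triggers the switch to 2 L, and the switch raises PaO₂. The measurement condition therefore depends on the quantity being measured, and it can differ between visits in the same patient. Since entrants are already on supplemental oxygen, desaturation on room air is plausible in a fair number of them.

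Nothing in the plan requires the condition to be recorded with the sample, to be the same at each visit, or to enter the analysis. At stake is the reading of the PaO₂ result. A mean change near zero could reflect stable oxygenation or could be produced by the sampling rule, and a larger sample would not separate the two. If the condition is not recorded when the sample is taken, the problem may be impossible to repair afterwards.

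**Working it through.** The documents give no mean, SD or expected change for PaO₂, so there is no plan figure to reproduce. The visits, the rule, the analysis and the 30 evaluable subjects come from the documents. Every PaO₂ value below is an assumption.

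**One patient.** Let g be the PaO₂ gain from 2 L.

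- Room air then 2 L: scored change = true change + g. With room-air values of 58 at baseline and 50 at Day 90 and g = 12, the Day 90 sample reads 50 + 12 = 62. Scored change is 62 − 58 = +4; true change is 50 − 58 = −8.
- 2 L then room air, the mirror case: baseline reads 50 + 12 = 62 and Day 90 reads 58. Scored change is −4; true change is +8.
- Same condition at both visits: g cancels.

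**Group mean.** Bias = k × g / 30, where k is the number moving from room air to 2 L minus the number moving the other way. For g from 5 to 25 mmHg:

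- k = 3 gives 3 × 5 / 30 = 0.5 to 3 × 25 / 30 = 2.5 mmHg.
- k = 6 gives 1.0 to 5.0 mmHg.

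**Simulation A, footnote at both visits.** Between-patient SD 8, visit noise SD 4, switch to 2 L below 55 mmHg, and a shift of −5 mmHg for every patient. Observed mean change:

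| Baseline mean | g = 8 | g = 12 | g = 18 |
|---|---|---|---|
| 55 | −3.31 | −2.46 | −1.16 |
| 60 | −3.30 | −2.45 | −1.16 |
| 65 | −3.75 | −3.12 | −2.20 |

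The share of the fall that is lost runs from 1 − 3.75/5 = 25% to 1 − 1.16/5 = 77%. About 17% to 24% of patients go from room air to 2 L. Among patients whose room-air value fell, 8% to 28% are scored unchanged or improved. With a true +5 the observed mean is +1.2 to +4.3, so gains shrink as well.

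**Simulation B, different assumptions.** Baseline mean 58, SD 8, SD of true change 6, switch below 55 or 60, g = 10 to 20, true mean −5. With the footnote at both visits, the observed mean is −3.4 to −0.5. Of patients who truly worsened, 15% to 31% are scored unchanged or improved; of those who truly improved, 12% to 16% are scored worse. For g = 15 and a switch below 55, 25.2% move from room air to 2 L and 2.5% move back, so −5.01 + 15 × (0.252 − 0.025) = −1.6, which matches the simulated mean.

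**Simulation B, baseline on oxygen.** If every baseline sample is on oxygen with the same gain, one reading of the baseline paragraph, and the footnote applies only at Day 90, the observed mean is −13.4 to −7.4 against a true −5. No worsened patient is then scored as improved. The direction of bias has reversed.

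**The case against.** PaO₂ is not a primary endpoint. Section 10(f) names tolerance and hours of use, and 10(i) says that this is not an efficacy trial. The abstract notes that long-term gas-exchange data are lacking, but it states the study's aim as safety and feasibility. All of this stands and limits the point to one stated, non-primary analysis. The claim that the condition goes unrecorded also rests on the plan's silence; the case report form is not among the documents.

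Three stronger readings are tempting and are not supported.

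- A reader might infer that the rule hides deterioration in the sickest patients. In simulation A, 11% to 48% of patients are below the switching point at both visits and are compared like with like. Those misread from room air to 2 L are borderline, with a mean baseline of about 59 to 61 mmHg. With a baseline mean of 55 or 60, none of the lowest baseline quartile is among them.
- A reader might infer that these switchers truly fell by about 9.5 mmHg, their mean room-air difference in simulation A. Every patient in that model shifts by exactly −5. The other 4.5 or so is selection on visit noise.
- A reader might infer that the bias always flatters the therapy. Under the footnote it shrinks gains and falls alike, and with baseline on titrated oxygen it can point to worsening.

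It is also fair to object that restricting the analysis to same-condition pairs is no cure. That selects on the outcome: in simulation A such pairs average −3.9 to −4.2, not −5.

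**Conclusion.** The concern holds in a bounded form. An oxygenation-triggered exception, decided separately at each visit and absent from the analysis, can misstate PaO₂ change for any patient whose condition differs between visits. That conclusion is arithmetic and needs no simulation. If the footnote governs all three visits, mean change is attenuated in both directions, with a true −5 mmHg observed as roughly −3.8 to −1.2 under the simulation A assumptions. That range is an illustration and depends on the assumed SDs, switching point and oxygen gain. If baseline is on titrated oxygen, the direction can reverse, so neither its sign nor its size can be fixed until the passages agree. The feasibility conclusions on tolerance and hours of use do not depend on it. The point merits correction because PaO₂ change is a named analysis and the remedy is cheap.

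**What to change.** 1. Reconcile the texts in 10(g) (figure notes, schedule footnote, baseline paragraph, Day 90 list and procedure paragraph) on the sampling condition at each visit and on whether the 2 L exception applies. Which rule to adopt is for the sponsor and investigator; this review does not choose one.
2. Record the inspired oxygen condition with every blood gas.
3. State in 10(f) and 10(i) that raw PaO₂ change will not be pooled across mixed conditions.
4. Report the number of patients changing condition in each direction as a result in its own right.
5. Analyse PaO₂ with all patients included by a method that uses the condition. One example is a paired rank analysis in which room air to oxygen counts as worse and the reverse as better. This works only if one sampling rule covers every visit. If baseline differs by design, a change of condition carries no such meaning and change from baseline stays confounded with inspired oxygen.
6. Show numeric change in same-condition pairs as descriptive only, labelled as a selected subset that understates change.
7. Report PaCO₂ and pH with the sampling condition noted.

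The cost is one data field and a few sentences, with no extra procedure or patient. The downsides are a rank-based result less familiar than a mean in mmHg, and its dependence on how consistently a discretionary exception without a threshold is applied in an open-label study.
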